As patients with postoperative COVID-positive status are difficult to interpret due to variable incubation period and the possibility of COVID-19 contraction while in hospital post-operatively, we will perform sensitivity analysis using alternative definitions for the COVID-positive cohort, including 1) rows 2, 4, and 6 (i.e. laboratory confirmed preoperatively or post-operatively), 2) rows 4 and 6 (i.e. laboratory confirmed or symptomatic preoperatively), and 3) rows 2, 3, 4, 5, and 6 (i.e. suspected and laboratory confirmed anytime preoperatively or post-operatively).

Table 1

Row #	NSQIP classification	
	Preoperative COVID (within 14 days before surgery)	Postoperative COVID
1	No	No
2	No	Yes – lab confirmed
3	No	Yes – suspected
4	Yes – lab confirmed	No
5	Yes – suspected*	No
6	Yes – suspected	Yes – lab confirmed

*Suspected denotes COVID-19 infection suspected by patient preoperative pneumonia or dyspnea

Outcomes

All outcomes (please see Appendix 1 for detailed definitions) will be measured within 30 days postoperatively, with the exception of length of stay (LOS) which was the total number of days from the day of operation to the day of discharge from hospital (19).

Primary outcomes

The primary outcome is all-cause 30-day mortality following hip fracture surgery.

Secondary outcomes

Secondary outcomes are MI, stroke or cerebrovascular accident (CVA), postoperative delirium, pneumonia, acute renal failure, transfusion, being on ventilator postoperatively (>48 hours), being still in hospital >30 days, length of stay (LOS), discharge destination as home versus not home, hospital readmission, and unplanned reoperation. There will be three composite outcomes: 1) venous thromboembolism (VTE), defined as pulmonary embolism or deep venous thrombosis, 2) sepsis, defined as sepsis or septic shock, and 3) any complication listed above or death. The definitions of secondary outcomes collected from NSQIP variables are included in Appendix 1 (Data Extraction Form).

Exposure

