The exposure to either SA or GA will be modelled as a binary variable (please see Appendix 1 for detailed definitions). SA will be defined as having either spinal or managed anesthesia care (MAC) documented the primary anesthesia technique, without GA secondary anesthesia technique. In NSQIP, regional anesthesia with MAC would be coded as MAC for the principal technique. Since it is highly unlikely that patients can tolerate hip fracture repair under sedation alone, MAC is counted as SA for the analysis. Those receiving both SA and GA (presumably either failed spinal and/or conversion to GA for other purposes) will be excluded from the primary analysis, but included in *a priori* sensitivity analysis with cohort characteristics displayed as a third comparison group, and analyzed as part of the GA group for the multivariable logistic regression.

Confounders

We selected an *a priori* list of potential confounders to adjust for the choice of anesthetic technique, based on availability within NSQIP, literature, clinical experience, and consensus within our multidisciplinary team. The confounders are: age, sex, race, body mass index (BMI) (calculated from height and weight in NSQIP), American Society of Anesthesiologists (ASA) Physical Status (PS), smoker within one year preoperatively, severe obstructive chronic pulmonary disease (COPD), dyspnea, coagulopathy (bleeding disorders), congestive heart failure (CHF), hypertension on medications, preoperative renal failure (acute renal failure, dialysis, and/or GFR < 60 mL/min/1.73 m² based on preoperative creatinine) (25), diabetes, preoperative functional status, preoperative delirium or dementia, systemic sepsis, total operating time, and days from hospital admission to operation. The definitions of potential confounding variables collected from NSQIP variables are included in Appendix 1 (Data Extraction Form). Since some of the potential confounders may provide similar information, collinearity will be assessed and variables will be combined or eliminated as described in the statistical analysis plan below.

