We acknowledge that NSQIP is missing several important confounders, particularly in terms of having little clinical information indicating the severity of COVID infection, such as the extent of oxygen requirements or admission to higher monitoring settings. In NSQIP, “a patient who is prescribed supplemental oxygen and utilizes it on a regular basis would be assigned as dyspnea upon moderate exertion unless there is documentation of dyspnea at rest”.

Statistical Analysis

1. Preprocessing
 1. Convert age from the NSQIP character variable to continuous variable, with Age “90+” recoded as 90
 2. Standardizing the coding of missing values: missing coded in NSQIP as “-99”, “unknown”, “None Assigned”, or “NULL”. Each variable will be individually examined to ensure that the missing value is correctly standardized.
 3. Missing values
 - Patients with missing data on key variables will be excluded as described in the inclusion/exclusion criteria.
 - For confounders in modeling, if
 1. >10% missing then exclude the confounder from the model
 2. <1% missing then delete case (complete case analysis)
 3. >=1% and <10% missing then multiple imputation

- The % of missing data for height and weight will be examined in cohort characteristics. If <1% is missing, then BMI will be calculated using these variables.

4. Check for collinearity with variance inflation factor and correlation matrix: if present, combine information from collinear variables if feasible (e.g. new variables is “yes” if “yes” in any of the variables); if not, eliminate the variable that has more missing values or would be less accurately ascertained
2. Descriptive statistics
 1. Cohort characteristics (perioperative and morbidity/mortality outcomes), including by 1) COVID-positive patients by SA vs. GA, 2) COVID-negative patients January-December 2021 vs. 2017-2019, 3) COVID-positive vs. negative in January-December 2021 stratified by anesthesia technique, and 4) utilization of SA vs. GA in 2021 (January-December) vs 2017-2019. Continuous variables will be presented as mean (standard deviation) and median (IQR) for parametric and nonparametric data, respectively. Categorical variables will be presented as frequency (%). For comparison amongst groups, ANOVA will be used for parametric data, Kruskal-Wallis for nonparametric data, and Chi-square for categorical data. Standardized mean difference will be presented.
3. Multivariable logistic regression

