 1. To assess the association amongst anesthesia type and mortality in COVID-positive patients, a multivariable logistic regression will be performed using a priori exposure (SA vs. GA) and confounder variables (above) for the primary outcome of mortality. The same independent variables will be used in the multivariable logistic regressions for secondary outcomes (linear regression with log transformation for the outcome of length of stay).
4. Sensitivity and exploratory analysis include
 1. We will define the COVID-positive cohort using the additional definitions discussed above per Table 1.
 2. Cohort characteristics of the GA + SA group will be presented, and compared to the SA and GA groups. If this group consists of >1% of the respective cohort, the multivariable logistic regression for mortality will be repeated with GA+SA included as part of the GA group for the multivariable logistic regression.
 3. Repeat the primary modeling with the cohort after excluding patients with age “90” (all patients aged 90 and above are coded as 90+ in NSQIP, thus potential residual confounding)
 4. If there is sufficient sample size, subgroup analysis by sex (male only, female only) and age (<65, >=65 year old) may be performed.
 5. The degree of unmeasured confounding will be assessed using E-value and the Durbin-Wu-Hausman test.
 6. Adjustment for multiple testing for secondary outcomes, including Bonferroni, False Discovery Rate, and Holm's method
5. Sample size calculation
 1. There are approximately 10,000 patients in the NSQIP Hip fracture dataset per year. The prevalence of COVID-19 in the hip fracture patient population was 10% (thus an estimated sample size of approximately 1000 patients) (<https://www.ncbi.nlm.nih.gov/pmc/articles/PMC7495188>), with a mortality

of 36% in this population. The pre-pandemic SA:GA utilization ratio was approximately 1:4 (20). With 80% power and 0.05 alpha, the sample size required to detect a 10% absolute decrease in mortality rate with the SA exposure (from 36% to 26%) is 1064, and 525 for 14% absolute decrease in mortality rate, as calculated by the Sample Size Calculator (<https://clinicalcalc.com/stats/samplesize.aspx>).

2. For population cohort studies where logistic regression is used, the sample size recommended is at least 500 patients, or $100 + 50i$ (i =number of independent variables in the final model) (26). With an estimated sample size of 1000 patients, 18 independent variables can be included.

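### Every binary secondary outcome gets the same full-covariate logistic model with no rule for few events, so a rare outcome may give no finite SA odds ratio

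*Combined protocol and SAP*

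**What the plan says.** Statistical Analysis item 3 fits a multivariable logistic regression for mortality in COVID-positive patients, using the SA/GA exposure and the confounders listed under Confounders. It then says: "The same independent variables will be used in the multivariable logistic regressions for secondary outcomes". Length of stay is the only outcome given a different model. The Confounders section names 18 variables, so the model as listed has 19 terms.

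The outcomes cover a wide span: "Secondary outcomes are MI, stroke or cerebrovascular accident (CVA), postoperative delirium, pneumonia", followed by acute renal failure, transfusion, ventilation beyond 48 hours, readmission, reoperation and others, plus composites for VTE, sepsis, and any complication or death. No expected rate is given for any of them.

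Two rules in item 1 (Preprocessing) can remove a variable: ">10% missing then exclude the confounder from the model" and "Check for collinearity with variance inflation factor and correlation matrix". Neither depends on the number of events. Item 4 makes subgroup analyses conditional on adequate sample size but sets no similar condition for secondary outcomes. Item 2 already plans "Cohort characteristics (perioperative and morbidity/mortality outcomes), including by 1) COVID-positive patients by SA vs. GA", with categorical variables as frequencies.

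**The concern.** A logistic model with 19 or more parameters needs enough events, not only enough patients. If none of the SA patients has the outcome, the maximum-likelihood SA coefficient runs off to minus infinity and no usable odds ratio exists. With few but non-zero events the estimate is finite but tends to lie too far from an odds ratio of 1.

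Morbidity is the stated secondary objective, and the study is to be registered before analysis. If a sparse outcome fails to fit and no rule exists, any change of method or of covariates is chosen after the result is seen. There is also a knock-on effect. In simulated separated fits the Wald |z| for SA was below 0.002, so p is about 1. If Wald p-values are used, an outcome with no SA events would enter the planned multiplicity adjustments as if it showed no association.

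**Working it through.** **Inputs from the documents.** Item 5.1: about 10,000 patients a year × 10% COVID-positive = 1000. Item 5.3 considers 500 to 1000. SA:GA is 1:4, so SA is 20% of N: 200 patients at N = 1000, 100 at N = 500. Mortality is 36% under GA and 26% under SA in the main scenario.

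**The plan's own figures.** A two-sided comparison of proportions without continuity correction gives 852 + 213 = 1065 for 36% v 26% (stated 1064) and 421 + 106 = 527 for 36% v 22% (stated 525). These agree closely. Item 5.2's model size is (1000 − 100)/50 = 18, as stated. That rule counts patients, so it says nothing about rare events.

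**Assumptions.** Secondary event rates of 1%, 2%, 5% and 10%; a true SA odds ratio of 1 or 0.6.

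**Step 1: chance of no SA events.** The formula is (1 − r)^(0.2N), where r is the rate among SA patients. For an odds ratio of 1, r is the overall rate. For 0.6, r is solved so that the overall rate is 1%, 2% or 5%, giving 0.655%, 1.314% and 3.324%. For example, 0.99^200 = 0.134 and 0.99345^200 = 0.27.

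| Overall rate | N = 1000, OR 1 | N = 1000, OR 0.6 | N = 500, OR 1 | N = 500, OR 0.6 |
|---|---|---|---|---|
| 1% | 13% | 27% | 37% | 52% |
| 2% | 2% | 7% | 13% | 27% |
| 5% | about 0% | 0.1% | 0.6% | 3% |

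A larger SA share lowers these. At 1%, N = 1000 and OR 1, a 30% share gives 0.99^300 = 4.9% and a 40% share gives 0.99^400 = 1.8%.

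**Step 2: separation of the SA coefficient in the full model.** Simulation with 1000 datasets per setting, true OR 0.6 and assumed covariate prevalences. The model has 19 parameters, or 25 if race has 4 levels and ASA status, dyspnea, diabetes and functional status have 3 each: 1 + 4 + 9 + 3 + 2 + 2 + 2 + 2 = 25.

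| Rate | N = 1000 (19 / 25 parameters) | N = 500 (19 / 25 parameters) |
|---|---|---|
| 1% | 26% / 30% | 59% / 69% |
| 2% | 7% / 8% | 27% / 27% |
| 5% | 0.2% / 0.2% | 3% / 4% |
| 10% | 0% / 0% | 0.1% / 0% |

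A separate simulation with 23 coefficients gave 32%, 10%, 0.3% and 0% at N = 1000, and 71%, 33%, 4% and 0.3% at N = 500.

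**Step 3: bias where the fit is finite.** True log OR = ln 0.6 = −0.51.

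| Setting | Ordinary fit, mean | Firth, mean | RMSE, ordinary v Firth |
|---|---|---|---|
| 5%, N = 1000 | −0.61 to −0.63 | −0.53 | 0.51–0.53 v 0.45–0.47 |
| 10%, N = 500 | −0.61 to −0.63 | −0.52 | 0.53–0.55 v 0.46–0.47 |
| 10%, N = 1000 | −0.56 to −0.57 | −0.52 | not quoted |

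Other runs gave slightly smaller means (for example −0.59 at 5%, N = 1000), so the excess is roughly 10% to 20%. Across repeat runs the medians were −0.52 to −0.60 against means of −0.55 to −0.63, so part of the excess is a skewed tail. Wald coverage of the finite fits was 95–96% at N = 1000.

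**Step 4: primary outcome.** At N = 1000, deaths are 800 × 0.36 + 200 × 0.26 = 340, or 17.9 per parameter with 19 and 13.6 with 25. At N = 500 there are 170 (8.9 and 6.8). The SA coefficient never separated in 200 runs per setting. The simulated mean log OR was about 3–5% too far from zero at N = 1000 and 5–9% at N = 500 (truth −0.471).

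**The case against.** The strongest reply is that the harm rests on rates the documents do not give. At N = 1000, separation matters only near 1–2%, the plan already pools some outcomes into composites, and the 1:4 ratio is pre-pandemic. MAC is counted as SA, and 2021 utilization is itself something the study will describe, so the SA share could be larger. All of this stands, and it is why the figures are given as conditional ranges.

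The bias at 5–10% is also modest. A mean log OR of −0.61 corresponds to an odds ratio of about 0.54 instead of 0.60, against an RMSE of about 0.5 in the sparser settings. That is small beside the unmeasured confounding the plan acknowledges. This too stands.

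The documents do not support four stronger readings that a reader might infer:

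- That named outcomes such as MI or stroke will fail to fit. Their rates are not given.
- That the analyst would be forced to change the method. A non-estimable result could be reported beside the SA and GA frequencies already planned in item 2. The gap is that no choice is fixed in advance.
- That the primary mortality model is undermined. It does not separate at the planned rates, although it is not wholly free of the same small bias.
- That 19 terms breach item 5.2. The rule is worded as at least 500 patients or 100 + 50i, refers to the final model, and counts patients. It has no bearing on sparse events.

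**Conclusion.** The point holds as a gap in the plan for binary secondary outcomes. The rule as written applies the same model whatever the event count and has no fallback. If an outcome occurs in about 1–2% of patients, the chance of no finite SA odds ratio is material, and at N = 500 it is large. At 5% the chance of no SA events is near zero at N = 1000 and about 1–3% at N = 500. At 5–10% the remaining effect is a modest exaggeration of the estimate.

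The zero-event figures depend only on N, the SA share, the true odds ratio and the assumed rate. The simulated figures also depend on assumed covariates and factor levels. That the planned fit is ordinary maximum likelihood is inferred from the absence of any other named method. Severity is minor to moderate and confined to secondary outcomes.

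**What to change.** Add to Statistical Analysis item 3, for binary secondary outcomes only:

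> If the rarer outcome category has fewer than 5 events per estimated parameter, or if separation or non-convergence occurs, Firth penalised logistic regression with the same covariates and profile penalised-likelihood intervals replaces the ordinary fit. Where confounders are multiply imputed, the penalised likelihood profiles are combined across imputations. SA and GA event counts are shown beside each odds ratio, and results with very few events are described as imprecise.

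Parameters should include the exposure, each continuous term and every non-reference factor level. The trigger is then 5 × 19 = 95 events, or 5 × 25 = 125. The imputation sentence is needed because item 1 plans ">=1% and <10% missing then multiple imputation". The primary mortality model stays as planned.

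The cost is a few sentences, no new data, and a pooling step for intervals. The downsides should be stated:

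- The threshold of 5 is a convention. At 10% and N = 1000 with 19 parameters there are 100/19 = 5.3 events per parameter, so the ordinary fit is kept although its mean is about 10% too far from zero.
- Firth supplies a finite estimate and a rule fixed in advance, but no information. At about 10 events the RMSE of the SA log OR is still about 0.8.
- Shrinkage can be material. At a 1% rate the mean Firth log OR was 0.83 times the truth at N = 1000 and 0.34 times at N = 500.
- Firth with Wald intervals covered only 88–92% at 10 or fewer events, which is the reason for profile intervals. The coverage of the profile intervals was not simulated.

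### The log-linear length-of-stay model either counts an in-hospital death like a discharge or becomes an unlabelled survivor-only comparison, in a cohort planned at 36% mortality

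*Combined protocol and SAP*

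**What the plan says.** Statistical Analysis, item 3 (Multivariable logistic regression) carries the covariates of the mortality model over to logistic models for the secondary outcomes, with one exception: "linear regression with log transformation for the outcome of length of stay".

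The Outcomes section gives LOS its own time window. All outcomes "will be measured within 30 days postoperatively, with the exception of length of stay (LOS) which was the total number of days" between operation and discharge. It does not say what value a patient takes who dies before discharge.

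The secondary outcomes also include "being still in hospital >30 days, length of stay (LOS), discharge destination as home versus not home, hospital readmission, and unplanned reoperation". Death enters a secondary outcome explicitly only in the third composite (any complication or death).

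Two other places could bear on the point:

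- Secondary outcomes refers the reader elsewhere: "The definitions of secondary outcomes collected from NSQIP variables are included in Appendix 1 (Data Extraction Form"). That appendix is not in the supplied text.
- Preprocessing, item 3, says: "Patients with missing data on key variables will be excluded as described in the inclusion/exclusion criteria". The exclusion criteria name anesthetic technique, ASA class V, preoperative ventilator dependence and coagulation limits. They name no outcome and exclude nobody for dying. The percentage thresholds that follow apply to confounders.

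**The concern.** LOS is meant to show whether patients recover and leave hospital sooner. A model on log days has no place for a patient who never leaves alive, and there are two ways to run it.

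- **Keep everyone.** The day of death closes the stay. An early death then scores as a short stay, the same as a quick recovery, and a late death scores as a long one. If SA changes only mortality, the LOS ratio still moves, up or down according to whether deaths come earlier or later than discharges. A death on the day of operation gives 0 days, which has no logarithm, although any zero-day stay has that difficulty.
- **Drop the dead.** The comparison is then among survivors only. If anesthetic technique affects survival, the two survivor groups are selected differently, and the plan attaches no label or caution.

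The secondary objective is lower morbidity with SA, so an LOS ratio on either side of 1 would be read as evidence about recovery.

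The same question, in milder form, affects three binary outcomes. Discharge home depends on where deaths are placed. Readmission and still in hospital beyond 30 days count a patient who has already died as event-free, which can make the group with better survival look worse.

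**Working it through.** **Inputs from the plan (Sample size calculation, item 1).** About 1000 COVID-positive patients, SA:GA 1:4 (200 and 800), mortality 36% under GA, reductions of 10 or 14 points under SA, 80% power, alpha 0.05.

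**The plan's own figure.** Two-sided, pooled variance, no continuity correction, 26% vs 36%, pooled proportion (0.26 + 4 × 0.36)/5 = 0.34:

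n(SA) = [1.96 × √(1.25 × 0.34 × 0.66) + 0.8416 × √(0.26 × 0.74 + 0.36 × 0.64/4)]² / 0.10² = 212.8

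Five times this is 1064, as the plan states (1065 after rounding up to 213 + 852). The inputs are therefore read as the plan intends.

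**Patients affected.** 200 × 0.26 + 800 × 0.36 = 52 + 288 = 340 deaths in 1000. The 36% is 30-day mortality, so it is an upper bound on deaths in hospital within 30 days. Let f be the share of those deaths that occur in hospital; f = 1 and f = 0.6 are shown.

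**LOS if death ends the stay.** Assumptions not in the documents: lognormal stay, median 7 days and log-SD 0.6, identical in both groups for patients not dying in hospital; lognormal in-hospital death times with the same log-SD. SA changes mortality only. Without truncation,

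ratio SA/GA = exp[f × mortality difference × ln(7 / median death day)]

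For example, exp[0.10 × ln(7/3)] = 1.09 and exp[0.06 × ln(7/3)] = 1.05. Simulation with death times truncated at day 30, 1,000,000 patients per group, 10 points:

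| Median death day | Ratio, f = 1 | Ratio, f = 0.6 | 5% test rejects, f = 1 | After Bonferroni over 15, f = 1 |
|---|---|---|---|---|
| 3 | 1.09 | 1.05 | 32% | 8% |
| 5 | 1.03 | 1.02 | 10% | 1% |
| 7 | 1.00 | 1.00 | 5% | 0.3% |
| 9 | 0.98 | 0.99 | 7% | 0.7% |
| 12 | 0.95 | 0.97 | 16% | 2% |

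A repeat simulation agreed to within 0.01 on the ratios and 1 percentage point on the rejection rates. At 14 points the ratio runs from 1.13 to 0.94 (f = 1) or 1.07 to 0.96 (f = 0.6). The 15 outcomes are the 12 single and 3 composite secondary outcomes listed.

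**LOS if the dead are dropped.** The ratio is 1.00 here, but only because identical survivor stays were assumed. In general, conditioning on survival can introduce its own bias.

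**Discharge home.** Assume 30% of patients not dying in hospital go home. With deaths as not home and f = 1: SA 0.74 × 0.30 = 22.2%, GA 0.64 × 0.30 = 19.2%, OR for home = (0.222/0.778)/(0.192/0.808) = 1.20. With f = 0.6: 25.3% vs 23.5%, OR 1.10. Leaving deaths out gives 1.00.

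**Readmission and still in hospital beyond 30 days.** With equal risk among those not dying in hospital and deaths kept as non-events, RR = (1 − f × 0.26)/(1 − f × 0.36) = 0.74/0.64 = 1.16 (f = 1) or 0.844/0.784 = 1.08 (f = 0.6).

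**Behaviour of the alternative.** Time to discharge alive, followed to day 30, 10 points, median death day 3, 7 and 12. The subdistribution hazard ratio is 1.27 throughout (f = 1) or 1.16 throughout (f = 0.6). The cause-specific ratio is 1.04, 1.15, 1.22 (f = 1) or 1.02, 1.07, 1.12 (f = 0.6). Neither changes direction with death timing.

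**The case against.** **Appendix 1 may hold the rule.** This stands, and it is why a reader should not infer that the plan has no rule for deaths: the supplied text cannot show that. But a coding rule would settle only which of the two readings of log LOS applies. One treats death as discharge and the other conditions on survival.

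**The other outcomes are already defined.** This largely stands. A reader might infer that readmission and still in hospital beyond 30 days are as ill-defined as LOS. They are not: nobody is excluded for dying, so the natural reading is a 30-day risk among all operated patients, and an RR of 1.16 is a true difference in that risk. What is missing is a label and a companion result. Likewise, placing deaths in the not-home category is a legitimate coding, not an error. It only needs to be stated.

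**The effect is small and rests on assumptions.** Partly stands. The LOS distortion is about nil when deaths and discharges have similar timing, and every scenario needs a 10- to 14-point mortality effect, which the primary outcome and the composite including death are there to show. The plan also lists "Adjustment for multiple testing for secondary outcomes, including Bonferroni" and other methods, and Bonferroni cuts the 32% rejection rate to 8%. It does not correct a biased estimate.

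**The competing-risk result is itself driven by mortality.** This stands. When SA changes mortality only (10 points, all deaths in hospital, median death day 7), the subdistribution test rejects in about 73% of studies and the cause-specific test in about 34%, against 5% for log LOS. The competing-risk analysis is therefore no purer measure of speed of recovery. Its gain is a stable direction and a clear meaning.

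**Conclusion.** The concern holds for the log-LOS model. Run as written with all patients kept, it lets a mortality effect alone produce an SA/GA ratio between about 1.09 and 0.95 at 10 points (1.05 to 0.97 with 60% of deaths in hospital), with the sign set by death timing. Run on survivors, it is an unlabelled selected comparison. The mortality figures are the plan's. The survivor stay, its spread, the death days, the in-hospital share and the 30% going home are assumptions.

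For discharge destination, readmission and still in hospital beyond 30 days, the conclusion is narrower: state how deaths are counted and show a second result beside the first.

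A reader might go further and infer that the LOS result must be misleading. The documents do not support that, because they give no timing of deaths or discharges, and similar timing makes the distortion vanish. The primary outcome is unaffected. This should be changed before analysis, with medium confidence because Appendix 1 is unseen.

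**What to change.** Check Appendix 1 first, and bring any rule for deaths into the analysis plan. Then, in Statistical Analysis, item 3:

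1. Beside the log-LOS model, analyse time from operation to discharge alive up to day 30, the limit of mortality follow-up, with in-hospital death as a competing event and the same confounders. Show cumulative incidence by group. Name the effect measure in advance (subdistribution or cause-specific). State that it combines survival with speed of discharge and must be read beside the mortality result.
2. Restrict the log-LOS model to patients discharged alive, labelled survivor-only and descriptive. If discharge-alive status or timing of death is not in the dataset, report only this model, using patients known to be alive at day 30.
3. For discharge destination, fix one coding of deaths and show the survivor-only result beside it.
4. Keep readmission and still in hospital beyond 30 days as 30-day risks in all operated patients, labelled as such, each with a composite that includes death beside it.

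The cost is some plan wording and a little standard R code, plus a check that the needed variables exist, which the supplied text does not show. The downside is that measures including death partly repeat the primary outcome, and the competing-risk result is not a ratio of days.

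### The optional sex and age subgroups are set out as restricted fits with no interaction test, so they cannot show whether the spinal-versus-general effect differs

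*Combined protocol and SAP*

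**What the plan says.** The subgroup plan is one sentence in the Statistical Analysis section, item 4 (Sensitivity and exploratory analysis), sub-item 4. It opens with the condition that the sample size be sufficient, and continues: "subgroup analysis by sex (male only, female only) and age (<65, >=65 year old) may be performed". It does not say how large is sufficient, which covariates the subgroup models would contain, or how the strata would be compared.

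The primary model, in item 3 of the same section, has main effects only: "a multivariable logistic regression will be performed using a priori exposure (SA vs. GA) and confounder variables (above) for the primary outcome of mortality". The Confounders section lists 18 items, which makes 19 variables with the exposure. Adjustment for multiple testing (item 4, sub-item 6) is confined to secondary outcomes, and significance is set at P < 0.05 throughout.

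On model size, item 5 gives a guideline of at least 500 patients, or 100 + 50i for i independent variables in the final model, and concludes: "With an estimated sample size of 1000 patients, 18 independent variables can be included".

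**The concern.** The wording male only, female only, and below versus at or above 65, reads naturally as four fits, each restricted to one stratum. Each such fit tests the SA effect against zero. None tests the SA effect in one stratum against that in the other. With nothing else specified, the comparison a reader is left with is which strata fall below P = 0.05. That comparison depends heavily on stratum size, so a difference in significance can appear when the effect is the same in both.

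At stake is a secondary message, such as a statement that SA helps women but not men. The primary analysis is not touched.

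Stratum size is a further matter. If the full covariate list were carried into each fit, every covariate effect would be re-estimated in part of a cohort that is itself expected to number about 1000.

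**Working it through.** **Inputs from the plan (item 5 and the Table 2 assumptions).** N about 1000; mortality 36% under GA and 26% under SA; SA:GA 1:4; alpha 0.05. Sidedness is not stated, but two-sided testing reproduces the plan's figures.

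**Assumed.** Stratum splits of 50:50, 70:30 and 90:10, because the document gives no sex or age distribution.

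**Reproducing the plan's figures.** The two-proportion formula (two-sided, 80% power, no continuity correction) gives 1064.1 before rounding for 36% versus 26%, against 1064 stated. It gives 525.2 for 36% versus 22%, against 525 stated. The model-size rule gives (1000 − 100)/50 = 18 variables, as stated.

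**Standard error of the SA log odds ratio at N = 1000 (200 SA, 800 GA).** √[1/(200 × 0.26 × 0.74) + 1/(800 × 0.36 × 0.64)] = √(0.02599 + 0.00543) = 0.177. The log odds ratio is ln[(0.26/0.74)/(0.36/0.64)] = −0.471. A stratum with share f of the cohort has standard error 0.177/√f.

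**Power in each stratum, same true effect in all (two-sided Wald test).**

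| Stratum N | SE | 0.471/SE | Power |
|---|---|---|---|
| 900 | 0.187 | 2.52 | 0.712 |
| 700 | 0.212 | 2.22 | 0.603 |
| 500 | 0.251 | 1.88 | 0.467 |
| 300 | 0.324 | 1.45 | 0.307 |
| 100 | 0.560 | 0.84 | 0.134 |

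**Chance that exactly one of two strata is significant**, a(1 − b) + b(1 − a):
- 50:50: 2 × 0.467 × 0.533 = 0.50
- 70:30: 0.603 × 0.693 + 0.307 × 0.397 = 0.54
- 90:10: 0.712 × 0.866 + 0.134 × 0.288 = 0.66

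A two-proportion test instead of the Wald test gives 50%, 55% and 67%. Over absolute differences of 10 to 14 points, the same three splits, and covariate R-squared of 0 to 0.4 (N multiplied by 1 − R²), the range is 34% to 78%. A valid interaction test would hold false claims of difference near 5% per factor.

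**Power of the interaction test**, for 36% to 26% in one stratum and no effect in the other. The standard error of the difference in log odds ratios is the root of the sum of the two squared standard errors. At 50:50 that is √(0.251² + 0.233²) = 0.342, so the ratio is 0.471/0.342 = 1.38 and power is 28%. At 70:30 power is 24% to 25%, and at 90:10 it is 13% to 14%, depending on which stratum holds the effect. With R-squared of 0.4 these fall to about 19%, 16% to 17%, and 10%.

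**Model size if all covariates were carried over.** Sex is constant within a sex stratum, so those fits have 18 variables and the rule asks for 100 + 50 × 18 = 1000 patients. The age strata have 19, so 100 + 50 × 19 = 1050. No stratum of a 1000-patient cohort reaches either. The rule allows 12 variables at N = 700, 8 at 500, 4 at 300 and none at 100.

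**The case against.** The strongest reply is that the plan promises very little here. The subgroups are conditional on sample size, may be performed rather than will be, and sit under an exploratory heading. No study objective concerns effect modification by sex or age. The plan nowhere says that significance will be compared between strata, so the fits could serve as a descriptive consistency check. All of this stands, and it limits the weight of the point. It does not remove it: the condition has no threshold, and a larger sample would still not supply the missing comparison.

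A reader might also infer that the plan puts 19 variables into small strata, or that the cohort is already too small by the plan's own rule. The document does not support either as a statement of fact. The subgroup covariate set is not given, and the sex strata would have 18 variables. The list may also shrink: "collinearity will be assessed and variables will be combined or eliminated as described in the statistical analysis plan below", and confounders with more than 10% missing are dropped. The size guideline has a 500-patient alternative, which the expected cohort and an assumed 700-patient stratum would both meet. The model-size concern is therefore conditional. It bites mainly in a smaller stratum, such as an assumed 300 or 100 patients.

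Finally, interaction terms also cost parameters and have low power. That is true and belongs in the fix.

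**Conclusion.** The point holds as a minor one. If the subgroups are run as worded, they cannot show whether the SA effect differs by sex or age. With an identical true effect, exactly one stratum would be significant about 50% to 66% of the time. That range rests on N = 1000, 36% versus 26%, SA:GA 1:4, no covariate adjustment, and assumed splits from 50:50 to 90:10. Other effect sizes and R-squared values move the figure but leave discordance common.

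The document does not support saying that the subgroups will certainly be run, that the authors intend to compare p-values, or that overfitted stratum models are planned. The shortfall against 1000 or 1050 patients per stratum arises only if the full covariate set is reused without pruning and the 100 + 50i branch is applied. The primary conclusion is unaffected.

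**What to change.** Replace the restricted fits with the full-cohort primary model, one factor at a time:
- **Sex:** add an SA-by-sex term.
- **Age:** in a separate model, add an SA-by-age-group term and an age-group main effect, since the primary model carries age as a continuous variable.

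From each model, report the stratum-specific SA odds ratios and the interaction estimate with confidence intervals, plus the interaction p-value. State that no claim of differing effects will be made without interaction evidence. Say before analysis what counts as sufficient sample size.

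**Cost.** One extra parameter for sex and two for age. Starting from 19 variables, the 100 + 50i rule would ask for 100 + 50 × 20 = 1100 and 100 + 50 × 21 = 1150 patients. That is above the expected 1000, but well below the 2 × 1000 or 2 × 1050 implied by two full separate fits. Covariate effects are assumed common across strata. Interaction power is low (about 13% to 28% unadjusted for an effect confined to one stratum, and less with covariate R-squared), so the text should state that a non-significant interaction is not evidence of equal effects.
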